3.2 Secondary Endpoints

The secondary endpoints for the study are:

1. Transferrin, TIBC, UIBC and ferritin concentrations from PK samples collected on Day 1 and Day 10;
2. Non-transferrin bound iron (NTBI) concentrations from PK samples collected on Day 1 and Day 10; and
3. Haemoglobin concentration and absolute reticulocyte count from haematology samples collected at Screening and Day 10.

3.3 Safety Endpoints

The safety endpoints for the study are:

1. Adverse Events (AEs) - Treatment Emergent Adverse Events (TEAEs), Treatment Emergent Serious Adverse Events (SAEs) and TEAEs leading to premature discontinuation of study drug/PK assessments;
2. Clinical laboratory safety blood results at Screening and Day 10;
3. Changes in vital signs and 12-lead ECG; and
4. Concomitant medications.

4 STUDY ASSESSMENTS

4.1 Screening Visit and Baseline

Written informed consent was to be obtained from each subject/legal guardian on the Screening Visit before any study assessment or test was conducted.

Demographic information, including date of birth, race, ethnicity and gender, was to be recorded at the Screening Visit.

All current medical conditions, all medical history relevant to iron deficiency diagnosis regardless of onset and all clinically significant medical history from the past five years including all malignancies, sterilisations, hospitalisations and surgeries were to be collected at the Screening Visit. For female subjects of childbearing potential, the method of contraception was also collected at this visit.

Body weight and height were to be measured at the Screening Visit only. Body Mass Index (BMI) will be derived using height and weight as measured at the Screening Visit as:

$$BMI = \frac{Weight \ (kg)}{[Height \ (m)]^2}$$

4.2 Primary Pharmacokinetic Measurements and Variables

4.2.1 PK blood sampling

On study days 1 and 10, all subjects were to have baseline (pre-dose) PK blood samples collected immediately prior to Ferric Maltol dosing (0h). Subjects were then to have further PK blood samples collected at two additional times between 0.5h and 6h after dosing on Days 1 and 10; within each Ferric Maltol dose group (7.8 mg, 16.6 mg or 30 mg BID), the post-dose PK sample time collection windows were 0.5-1h, 1.0-2.0h, 2.0-3.0h, 3.0-4.0h and 4.0-6.0h. The 12 subjects within each Ferric Maltol dose group were assigned to the required post-dose PK blood sampling schedule in sequential order at the time of randomisation, based on current subject enrolment across all study sites. Table 3 details the sparse PK blood sample schedule.

Table 3 Sparse PK Blood Sampling Schedule

	PK Sample Schedule			
	Group 1 (N = 3/12)	Group 2 (N = 3/12)	Group 3 (N = 3/12)	Group 4 (N = 3/12)
Pre-dose (0h)	X	X	X	X
0.5 – 1h	X	X		
1.0 – 2.0h	X		X	
2.0 – 3.0h		X		X
3.0 – 4.0h			X	
4.0 – 6.0h				X

For each individual subject, the post-dose PK blood sampling schedule was to be the same on Day 1 and Day 10. Post-dose samples for each subject were to be collected within the allocated time-windows (e.g. between 0.5-1h or 1-2h); the exact time of the sample collection was to be recorded in the eCRF. For those subjects in PK Sample Schedule Group 1 (see Table 3), the PK blood samples for the 0.5-1h timepoint window were to be taken at 30 minutes prior to the PK blood samples for the 1-2h timepoint window on Day 1 and Day 10, to provide an adequate spread of actual sampling times for the population PK analysis.

4.2.2 PK Parameters

PK samples were to be collected on Day 1 and Day 10, pre-dose and post-dose according to the PK Sample Schedule Group that the subject was assigned to.

Maltol (ng/dL) and Maltol Glucuronide (µg/mL) results will be available from the data export from the bioanalytical laboratory, ABS Laboratories Ltd.

Serum iron (µmol/L) and TSAT (%) will be available from the standard export from Medpace Reference Laboratory (MRL). The data transport files from MRL will contain serum iron and

TSAT in the standard reporting units of the reporting laboratory and in Système International d'Unités (SI) units.

C_{\max} , $C_{\text{ave}(0-6h)}$, $AUC_{(0-6h)}$, $AUC_{(0-\infty)}$, T_{\max} , half-life ($t_{1/2}$), apparent systemic clearance (CL/F), apparent volume of distribution (V/F) and C_{trough} will be derived for maltol, maltol glucuronide, serum iron and TSAT at Day 1 and Day 10.

4.3 Secondary Endpoint Measurements and Variables

4.3.1 Iron Markers and Non-Transferrin Bound Iron (NTBI)

Iron markers include transferrin, total and unsaturated iron binding capacity (TIBC and UIBC) and ferritin. Iron markers and NTBI were to be collected on Day 1 and Day 10, pre-dose and post-dose according to the PK Sample Schedule Group that the subject was assigned to.

The following list of iron markers and NTBI will be available from the standard export from MRL:

- Transferrin (units) g/l
- TIBC (units) $\mu\text{mol/L}$
- UIBC (units) $\mu\text{mol/L}$
- Ferritin ($\mu\text{g/L}$) $\mu\text{g/L}$
- NTBI (units) <0.2 eLPI unit =negative, ≥0.2 eLPI unit=positive

The data transport files from MRL will contain iron markers in the standard reporting units of the reporting laboratory and in SI units. All iron markers will be converted to and reported using units indicated in parenthesis above.

Baseline for iron markers and NTBI is defined as the pre-dose value observed at the Day 1 Visit. Change from baseline to each post-baseline visit/timepoint will be derived for each parameter as visit/timepoint value minus baseline.

NTBI results will be available from the data export from Afferix Ltd.

4.3.2 Haemoglobin Concentration and Absolute Reticulocyte Count

Haemoglobin concentration and absolute reticulocyte counts were to be collected at the Screening Visit and on Day 10.

Haemoglobin concentration (g/dL) and absolute reticulocyte counts (10^6 Cells/ μL) will be available from the standard export from MRL. The data transport files from MRL will contain haemoglobin concentration and absolute reticulocyte counts in the standard reporting units of the

reporting laboratory and in SI units; values will be converted to and reported using units indicated in parenthesis above.

Baseline for haemoglobin concentration and absolute reticulocyte count is defined as the value observed at the Screening Visit. If the Screening retest is performed, the values of Screening retest will be used as baseline. Change from baseline to Day 10 will be derived for each parameter as visit value minus baseline.

4.4 Safety Measurements and Variables

4.4.1 Adverse Events

An adverse event (AE) is any untoward medical occurrence in a subject administered a pharmaceutical product and does not necessarily have a causal relationship with this treatment.

Any serious adverse event (SAE) that occurred from informed consent being obtained at the Screening Visit until two week after the last dose was to be recorded in the eCRF. Any AE that occurred from the time of dosing until the end of the study was to be recorded in the eCRF. The following details were to be recorded for each adverse event:

- Adverse event reported term;
- Start date and time and stop date;
- Outcome (fatal, ongoing/not resolved, recovered, recovered with sequelae, unknown);
- Severity (mild, moderate, severe);
- Relationship to study drug (related, not related);
- Action taken with study drug (dose increased, dose not changed, dose reduced, drug interrupted, drug withdrawn, not applicable, other, unknown);
- Other action taken, not related to study drug (none, concomitant medication required, non-drug therapy required);
- Cause study discontinuation (yes, no);
- Serious (yes, no); and
- If serious:
 - Death (yes, no);
 - Life-threatening (yes, no);
 - Inpatient hospitalisation (yes, no);
 - Prolongation of hospitalisation (yes, no);
 - Congenital anomaly or birth defect (yes, no);
 - Persistent or significant disability/incapacity (yes, no); and
 - Judged as medically significant (yes, no).

Adverse events will be coded using MedDRA version 19.0.

Adverse events defined as treatment emergent adverse events (TEAE) if they occur after the first dose intake of study drug. Treatment emergent adverse events will be identified by comparing the recorded start date and time of the event with the date and time of the first dose intake of study drug. Identification of the treatment emergent status of adverse events with a partial start date will be determined using the available incomplete date information. For example, if the adverse event has a missing day field but the non-missing month and year fields place the start of the event after the start of study drug, then the event will be assigned to the treatment emergent class. For adverse events where the available partial date information is inconclusive (for example, missing day but available month and year are equal to the month and year of start of study drug) then the event will be classified as treatment emergent. In particular, adverse events with a completely missing start date will be assumed to be treatment emergent (unless the stop date places the event prior to starting study drug).

4.4.2 Safety Clinical Laboratory Measurements

Routine clinical laboratory safety bloods for haematology and clinical chemistry evaluations were to be obtained at the Screening Visit and at Day 10.

4.4.2.1 Haematology

The following haematology parameters will be available from the standard export from MRL:

- Red blood cell count ($10^{12}/L$);
- Haematocrit (%);
- Mean cell volume (MCV) (fL) ;
- Mean corpuscular haemoglobin (MCH) (pg);
- Mean corpuscular haemoglobin concentration (MCHC) (g/L);
- White blood cell count (total and differential (% and absolute)) ($10^9/L$); and
- Platelet count ($10^9/L$).

The data transport files from MRL will contain haematology parameters in the standard reporting units of the reporting laboratory and in SI units; values will be converted to and reported using units indicated in parenthesis above.

Baseline for all haematology parameters is defined as the value observed at the Screening Visit. If the Screening retest is performed, the values of Screening retest will be used as baseline. Change from baseline to Day 10 will be derived for each parameter as visit value minus baseline.

4.4.2.2 Clinical Chemistry

The following clinical chemistry parameters will be available from the standard export from MRL:

- ALT (U/L);
- AST (U/L);
- Alkaline phosphatase (U/L);
- Gamma-glutamyl transpeptidase (GGT) (U/L);
- Total bilirubin (μmol/L);
- Creatinine (μmol/L);
- Amylase (U/L);
- Blood urea nitrogen (BUN) (mg/dL);
- Phosphorous (mg/dL);
- Sodium (mmol/L);
- Potassium (mmol/L);
- Chloride (mmol/L);
- Calcium (mmol/L);
- Total cholesterol (mmol/L);
- Uric acid (μmol/L);
- Glucose (mmol/L);
- Total protein (g/L); and
- Albumin (g/L).

The data transport files from MRL will contain clinical chemistry parameters in the standard reporting units of the reporting laboratory and in SI units; values will be converted to and reported using units indicated in parenthesis above.

Baseline for all clinical chemistry parameters is defined as the value observed at the Screening Visit. **If the Screening retest is performed, the values of Screening retest will be used as baseline.** Change from baseline to Day 10 will be derived for each parameter as visit value minus baseline.

4.4.2.3 Urine Pregnancy Test

For females of childbearing potential, a urine pregnancy test will be conducted at the Screening Visit, prior to first dose of study drug on Day 1, prior to study drug dosing on Day 10 and at the Follow-Up Visit.

For all Safety Clinical Laboratory measurements, values outside the reference range will be categorized as above (RH: Reference High) or below (RL: Reference Low) the reference range based on the Central Laboratory's normal reference range. Notable Low (NL), Notable High (NH), Critical Low (CL) and Critical High (CH) values will also be flagged.

4.4.3 Vital Signs

Body temperature (°C), diastolic and systolic blood pressure (mmHg) and pulse rate (beats/min) were to be assessed at the Screening Visit, pre-dose on Days 1 and 10 and at the Follow-up Visit.

For all vital signs parameters, baseline is defined as the pre-dose value on Day 1. If a pre-dose value at Day 1 is not available, the value from the Screening Visit will be used as the baseline value. Change from baseline to each post-baseline visit (Day 10 and Follow-up) will be derived as visit value minus baseline. Observed values and change from baseline will be summarized by dose group and visit/timepoint descriptively. Data will also be listed by dose group and visit/timepoint.

4.4.4 12-Lead ECG

A 12-lead ECG was to be recorded at the Screening Visit and at Day 10 (between 1h and 4h post-dose). Machine reported standard ECG parameters were to be recorded in the eCRF and include:

- Heart Rate (beats/min);
- PR Interval (msec);
- RR Interval (msec);
- QRS Duration (msec);
- QT Interval (msec); and
- Overall clinical interpretation (Normal, Abnormal, Indeterminate, Not Evaluable, Unknown).

The following additional parameters will be derived from the standard ECG parameters:

- QTcB Interval (msec), defined as:

$$QTcB = \frac{QT \text{ Interval}}{\sqrt{RR \text{ Interval}}}$$

- QTcF Interval (msec), defined as:

$$QTcF = \frac{QT \text{ Interval}}{\sqrt[3]{RR \text{ Interval}}}$$

For all ECG parameters, baseline is defined as the value observed at the Screening Visit. **If the Screening retest is performed, the values of Screening retest will be used as baseline.** Change from baseline (to Day 10) will be derived as visit value minus baseline. Observed values and change from baseline will be summarized descriptively by dose group and visit/timepoint. Data will also be listed by dose group and visit/timepoint.

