10.6 VITAL SIGNS AND 12-LEAD ECG

Body temperature (°C), blood pressure and pulse rate will be assessed at Screening, pre-dose on Days 1 and 10 and at Post-study; blood pressure and pulse rate should be measured after the subject has been supine for at least 5 minutes.

A 12-lead ECG will be recorded at Screening and again on Day 10 (between 1h and 4h post-dose). Machine reported standard ECG parameters (heart rate, PR interval, RR interval, QRS duration, QT interval) and overall clinical ECG interpretation will be recorded in the eCRF.

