10.3 Vital Signs

Vital signs data will be summarised by dose group and overall by visit (Screening, Days 1 and 10 and Follow-up) for the Safety Population. Change from baseline at each post-baseline visit (Day 10 and Follow-up) will be presented in a separate summary table and will include baseline, post-baseline values and change from baseline values for subjects with both baseline and specific post-baseline values. Baseline is defined as the last value observed before the first dose.

All vital signs data will be listed for the Screened Population and FAS/ITT Population.

10.4 12-Lead ECG Parameters

Continuous ECG parameters (Heart Rate, PR Interval, RR Interval, QRS Duration, QT Interval, QTcB Interval and QTcF Interval) will be summarised by dose group and overall by visit (Screening and Day 10) for the Safety Population. Change from baseline at Day 10 will be presented in a separate summary table and will include baseline, post-baseline values and change from baseline values for subjects with both baseline and Day 10 values. Baseline is defined as the last value observed before the first dose.

Overall interpretation will also be summarised by dose group and overall by visit. Shift tables (from baseline to Day 10) will also be generated for the overall interpretation results.

All ECG data will be listed for the Screened Population and FAS/ITT Population.

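### SAP 4.4.4 enters RR in msec in the QTcB and QTcF formulas without converting it to seconds, so applied as written the results are 31.6 and 10 times too small and are not in msec

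*SAP*

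**What the plan says.** SAP 4.4.4 (12-Lead ECG) lists the machine-reported parameters with their units. RR appears as "RR Interval (msec") and QT as "QT Interval (msec); and". The section then states: "The following additional parameters will be derived from the standard ECG parameters". Two formulas follow:

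- QTcB, introduced by "QTcB Interval (msec), defined as", is QT divided by the square root of RR.
- QTcF, also labelled msec, is QT divided by the cube root of RR.

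The same section adds: "Change from baseline (to Day 10) will be derived as visit value minus baseline".

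SAP 10.4 puts both derived values into the safety tables, in a list ending "QTcB Interval and QTcF Interval) will be summarised by dose group and overall by visit", with a separate change-from-baseline table for Day 10.

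Protocol 10.6 names what is recorded: "Machine reported standard ECG parameters (heart rate, PR interval, RR interval, QRS duration, QT interval"). It mentions no QTc, no units for the intervals and no conversion.

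**The concern.** The input unit, the formula and the output label cannot all be right. Dividing msec by the square root or cube root of msec does not return msec. The label is correct only when RR is a number of seconds, so that the denominator equals 1 at 60 beats/min and QTc equals QT there.

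These two lines are the only definition of QTc in either document. No machine-reported QTc is collected, so there is no recorded value to check against. The planned output is the absolute change from Screening to Day 10, and a scale error acts directly on it: a real shift of tens of msec would be tabulated as one or two units labelled msec. ECG change is a secondary endpoint in Protocol 6.4 and a safety endpoint in SAP 3.3.

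There is also a validation problem. A check of the program against the SAP text would mark correct code as a mismatch and incorrect code as a match.

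**Working it through.** **Inputs from the documents (SAP 4.4.4).** QT in msec; RR in msec; QTcB = QT / RR^(1/2); QTcF = QT / RR^(1/3); both outputs labelled msec. The plan states no numerical QTc value, so there is no figure of its own to reproduce.

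**Search for a conversion.** The protocol's ECG text (10.2, 10.6, 11.5, 12.2.2) and the SAP's (Table 2 footnotes, 3.3, 4.4.4, 10.4) contain none. By contrast, the SAP states conversion to its listed reporting units for haemoglobin and reticulocytes (4.3.2), haematology (4.4.2.1) and chemistry (4.4.2.2). Section 4.4.4 has no such sentence.

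**Units as written.**

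- QTcB: msec / msec^(1/2) = msec^(1/2)
- QTcF: msec / msec^(1/3) = msec^(2/3)

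**Size of the discrepancy.** Divide the value with RR in seconds by the value as written:

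- QTcB: [QT / (RR/1000)^(1/2)] / [QT / RR^(1/2)] = 1000^(1/2) = 31.62
- QTcF: [QT / (RR/1000)^(1/3)] / [QT / RR^(1/3)] = 1000^(1/3) = 10.00

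QT and RR cancel, so the factors are the same for every subject and visit.

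**Illustrations.** The documents give no QT or RR values, so those below are assumptions.

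| QT (msec) | RR (msec) | QTcB as written | QTcB, RR in s | QTcF as written | QTcF, RR in s |
|---|---|---|---|---|---|
| 400 | 1000 | 400/sqrt(1000) = 12.6 | 400/sqrt(1) = 400 | 400/1000^(1/3) = 40.0 | 400/1 = 400 |
| 400 | 800 | 400/sqrt(800) = 14.14 | 400/sqrt(0.8) = 447.2 | 400/800^(1/3) = 43.09 | 400/0.8^(1/3) = 430.9 |
| 410 | 750 | 410/sqrt(750) = 14.97 | 410/sqrt(0.75) = 473.4 | 410/750^(1/3) = 45.13 | 410/0.75^(1/3) = 451.3 |

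The first row is an internal check: at RR 1000 msec (60 beats/min) a corrected QT must equal the raw QT, and as written it does not.

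**Change from baseline.** Take row 2 as Screening and row 3 as Day 10:

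- QTcB: 14.97 − 14.14 = 0.83 as written; 473.4 − 447.2 = 26.2 msec with RR in seconds
- QTcF: 45.13 − 43.09 = 2.04 as written; 451.3 − 430.9 = 20.4 msec with RR in seconds

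Percentage changes are the same either way (5.9% for QTcB, 4.7% for QTcF), but the SAP plans no percentage-change table for ECG.

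A second assumed pair, QT 380 to 390 and RR 900 to 800 msec, gives a QTcB change of 1.12 against 35.5 msec and a QTcF change of 2.65 against 26.5 msec.

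**The case against.** The best counter-argument is that this is an omission of notation, not a wrong method. The SAP names the two corrections and fixes the output in msec, and that label already implies RR in seconds. A programmer may well convert by convention. The documents contain no program and no QTc output, so no actual error has been shown.

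A literal result would also be conspicuous. A QTcB of 14 labelled msec would sit in the same set of summaries as a QT of 400 msec, with RR and heart rate alongside, and it could be restored by a constant factor.

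Nor does anything turn on these values. QTc is an SAP addition that the protocol's ECG text does not mention. The SAP sets no QTc category, test or stopping rule. The investigator's overall reading has its own output ("Shift tables (from baseline to Day 10) will also be generated for the overall interpretation results"), and clinically significant ECG findings are reported as adverse events on the investigator's judgement (Protocol 11.1.1). Neither uses the formulas.

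All of this stands as a limit on the consequence. It does not rescue the text: the output label points one way, while the stated RR unit and the stated source of the inputs point the other.

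**Conclusion.** The point holds. As written, SAP 4.4.4 gives QTcB and QTcF values that are too small by factors of 31.6 and 10 and are mislabelled as msec, and the absolute changes in SAP 10.4 are reduced by the same factors. The factors follow from the units alone; only the worked QT and RR values are assumed.

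Whether any reported number is wrong depends on literal programming, which the documents cannot settle. The reach is two of the seven continuous ECG parameters, in descriptive tables and listings. The primary PK endpoints, the clinical ECG interpretation and adverse event reporting are untouched. The text should be corrected, but the point does not threaten the trial's conclusions.

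**What to change.** In SAP 4.4.4, with QT and RR both in msec, write:

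- QTcB = QT / sqrt(RR/1000)
- QTcF = QT / (RR/1000)^(1/3)

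Then confirm that the derivation program matches. A simple test is that a record with RR 1000 msec returns QTcB and QTcF equal to QT.

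The cost is a correction to two formulas and one check of the program. No new data and no further analysis are needed.

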4.4.5 Physical Examination

A brief physical examination was to be conducted at the Screening and Follow-up Visits. The examination was to include an assessment of general appearance, skin, head, eyes, ears, nose and throat, cardiovascular, respiratory, abdominal, gastrointestinal and musculoskeletal systems.

4.4.7 Study Drug Exposure and Compliance

Study drug was to be dispensed at the Day 1 Visit and returned at the Day 10 Visit or Early Termination Visit. The first dose intake of Ferric Maltol was to be taken on site during the Day 1 Visit and the last intake was to be taken on site on the morning of the Day 10 Visit after the pre-dose PK blood samples had been taken. All unused medication was to be returned at the Day 10 or Early Termination Visit. A record of the number of capsules dispensed and returned for each subjects was to be documented in the eCRF.

Compliance will be evaluated by comparing the expected number of capsules of study drug administered with the actual number of capsules of study drug administered during the open-label treatment period.

Assuming that the subject takes the first dose on the morning of Day 1 and the last dose on the morning of Day 10, the expected number of capsules taken is assumed to be 19 capsules (i.e. 2 capsules per day on Days 1 to 9 plus 1 capsule on the morning of Day 10). If the subject does not complete the open-label treatment period as planned then the expected number of capsules will be calculated taking into account the timing of the first and last doses.

The actual number of capsules taken will be derived as the difference in the number of capsules dispensed and returned as recorded in the eCRF.

Compliance will therefore be derived as:

$$\text{Compliance} = \frac{\text{Actual number of capsules taken}}{\text{Expected number of capsules taken}} \times 100\%$$

